(d) Clinical outcomes after SVG interventions are poor,⁵³ especially if SVGs are occluded at presentation. We recently reviewed the outcomes of 34 consecutive patients undergoing percutaneous intervention for acute SVG occlusion at our institution and found 86% procedural success compared to 99% success in native coronary artery lesions.⁹ At 1 and 3 years, mortality was 8% and 42%, an acute coronary syndrome occurred in 15% and 41%, and repeat coronary revascularization was required in 28% and 38%, respectively.⁹ Approximately half of the deaths were cardiac, and the remainder were non-cardiac (cancer, infection, stroke), which is likely explained by their advanced age and multiple comorbidities.

In summary, early SVG failure is common and carries significant morbidity and mortality. If prasugrel can prevent early SVG failure, it could significantly improve the quality and duration of life of patients undergoing CABG, reduce the need for repeat revascularization procedures, and potentially reduce their healthcare costs.

8. SUBJECT SELECTION, INCLUSION AND EXCLUSION CRITERIA:

Patients undergoing clinically-indicated CABG will be identified by a study investigator or coordinator and will be screened for eligibility for the study using the following criteria:

Inclusion criteria:

1. Age 18 years or greater
2. Willing and able to give informed consent. The patients must be able to comply with study procedures and follow-up.
3. Undergoing clinically-indicated coronary artery bypass graft surgery

Exclusion criteria:

1. Known allergy to aspirin or prasugrel
2. Need for concomitant cardiac procedure, such as valve repair or replacement
3. Increased risk of bleeding [need for warfarin or oral Xa inhibitor or thrombin inhibitor administration, recent (within 30 days) major bleed, known bleeding diathesis or coagulation disorder]
4. Positive pregnancy test or breast-feeding
5. Coexisting conditions that limit life expectancy to less than 12 months or that could affect a patient's compliance with the protocol
6. Serum creatinine > 2.5 mg/dL
7. Severe peripheral arterial disease limiting vascular access
8. Prior stroke or transient ischemic attack
9. Weight <60 kg or age >75 years
10. Multiple distal SVG anastomoses
11. Postoperative complications prolonging hospitalization (including, but not limited to bleeding, prolonged intubation, infection, deep venous thrombosis or pulmonary embolism)

9. NUMBER OF SUBJECTS IN THE STUDY:

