Approximately 120 patients will be randomized into this study at the Dallas VA Medical Center.

10. JUSTIFICATION FOR THE USE OF SPECIAL SUBJECT POPULATIONS:

Not applicable.

11. STUDY DESIGN:

The primary efficacy objective is to compare the prevalence of SVG thrombus as detected by optical coherence tomography of a target SVG between patients receiving prasugrel vs. placebo. We hypothesize that prasugrel will be superior to placebo in reducing the prevalence of SVG thrombus at 12-month follow-up OCT imaging.

The primary safety endpoint is the incidence of severe bleeding as defined using the GUSTO study criteria.⁶⁷ We hypothesize that patients receiving prasugrel will have similar incidence of severe bleeding compared to patients receiving placebo during the 12-month study period.

The secondary endpoints will be: (1) incidence of angiographic SVG failure (defined as $\geq 75\%$ SVG diameter stenosis in at least one SVG); the total and normalized total SVG atheroma volume within at least 40 mm of the target SVG, as assessed by intravascular ultrasonography; the lipid core burden index of the target SVG, as assessed by near-infrared intracoronary spectroscopy; and (2) the incidence of major adverse cardiac events and moderate bleeding during the 12-month study period.

The proposed study is a phase 3, single-center, randomized, double-blind, controlled, parallel-group study of prasugrel vs. matching placebo in patients with recent CABG, starting at the time of hospital dismissal from CABG (Figure 13). All patients will be receiving aspirin, as per standard current practice.

[figure not shown]

Figure 13: Flowchart of the proposed study design.

CABG = coronary artery bypass graft surgery; OCT = optical coherence tomography; IVUS = intravascular ultrasound; NIRS = near-infrared spectroscopy; R = randomization; m = month; FU = follow-up.

12. DESCRIPTION OF PROCEDURES TO BE PERFORMED:

The study design will be explained to the patients and if they agree to participate they will be asked to sign an informed consent form and they will receive a copy of the consent form. They will subsequently be randomized to prasugrel or placebo, as described below.

Randomization and Treatment

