One SVG will be examined in each patient. The target intermediate SVG lesion will be selected by the interventional cardiologist performing the procedure as the longest and least-angulated SVG amenable to intravascular imaging. After intragraft administration of 200 µg of nitroglycerin, an OCT catheter (DragonFly, St Jude Medical, Minneapolis, Minnesota) will be advanced 40-50 mm distal to the SVG proximal anastomosis and will be pulled back proximal to the lesion using a motorized system at a speed of 20 mm/sec. The OCT images will be written on CD-R or DVD for subsequent off-line analysis. Subsequently, a 45-MHz, 3.2F, rotational IVUS catheter (Revolution, Volcano therapeutics, Rancho Cordova, California, USA) will be advanced into the target SVG and the transducer will be advanced as distal as possible within the SVG and will then be pulled back to the SVG aortic ostium using a motorized pull-back system at a speed of 0.5 mm/s. During pullback, gray-scale IVUS will be recorded at a rate of 30 frames per second. The gray-scale IVUS movie will be written on CD-R or DVD for subsequent off-line analysis. Similarly, a 3.2-F near-infrared spectroscopy catheter (Lipiscan IVUS, InfraReDx, Burlington, Massachusetts) will be advanced into the target SVG and positioned to the same location where the IVUS catheter was previously placed, if feasible. The catheter will then be pulled back to the aortic ostium using a motorized pull-back system at a speed of 0.5 cm/s. A chemogram of the artery will be obtained, as shown in Figures 10-12. The near-infrared spectroscopy data will also be recorded in CD-R or DVD for subsequent analysis.

Examination of the target SVG lesion with angiography, OCT, IVUS, and NIRS will be obtained at 12 months post CABG. If the patient undergoes clinically-indicated graft angiography before the 12-month planned angiography, then: (a) if ≥ 10 months have elapsed from enrollment in the study, then angiography, OCT, IVUS, and NIRS of a target SVG will be performed; or (b) if <10 months have elapsed from enrollment, then prasugrel will be continued and the patient will be asked to return for the planned 12-month angiography, OCT, IVUS and NIRS.

Follow-Up: Study procedures and follow-up assessments are summarized in the below table 2.

Table 2. Schedule of observations and laboratory assessments.

Test	Treatment period						Post-Treatment Follow-up Contact (30 days after 12 month visit – Phone FU)

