	0	1m +/- 5 days	3m +/- 10 days (phone FU)	6m +/- 10 days	9m +/- 10 days (phone FU)	12m +/- 30 days	
Inclusion/Exclusion criteria reviewed	X						
Informed consent	X						
Medical history	X	X	X	X	X	X	X
Physical examination/ Vital Signs	X	X		X		X	
Medication adherence		X	X	X	X	X	
Electrocardiogram	X					X	
SVG angiography, OCT, IVUS and NIRS						X	

FU=follow-up; SVG=saphenous vein graft; IVUS=intravascular ultrasonography; NIRS = near-infrared spectroscopy; OCT = optical coherence tomography

13. ANTICIPATED DATA AND DATA ANALYSIS:

Expected treatment effect

A recent study demonstrated the presence of thrombus in 25% of SVGs examined early post CABG.⁴⁷ Given the potent antiplatelet effect of prasugrel, we anticipate 80% reduction in the prevalence of thrombus in SVGs, as assessed by OCT.

Sample size calculation

Assuming that thrombus will be detected by OCT in 25% of patients in the placebo group vs. 5% of patients in the prasugrel group (80% relative reduction), the sample size required to detect the specified difference with 80% power and a 2-sided α

level of .05 is 48 patients per group, which was increased to 60 patients to allow for 20% dropout.

Assuming 48 patients are evaluable in each group, the power of the study assuming a prevalence of thrombus by OCT in the control arm of 20%, 25%, and 30% will be 67%, 80%, and 89%, respectively.

Enrolling 40 patients per year for three consecutive years will require enrollment of 25 % of the eligible patients at our institution. Enrollment rate in the SOS trial which also required angiographic and IVUS follow-up⁶² was 56%, suggesting that enrollment of the projected number of patients is feasible in our setting.

Statistical Analysis of primary endpoints

All endpoints (primary and secondary) will be analyzed with an intent-to-treat approach.

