For safety monitoring, any emergency adverse event resulting from participation in the study will be treated at the Dallas VA Medical Center. [name] will evaluate all adverse events and determine the appropriate course of action.

If a patient develops severe bleeding during the study period, prasugrel will be temporarily held and will be discontinued if the patient is considered to be at increased risk for recurrent bleeding. If a patient develops an indication for receiving oral anticoagulation therapy with warfarin or dabigatran during his or her participation in the study, prasugrel administration will be discontinued to minimize the risk of bleeding.

If any subjects are hospitalized for an acute coronary syndrome or undergo coronary angiography at an outside hospital, the hospitalization records will be obtained and reviewed by the clinical events committee. The Universal definition of myocardial infarction will be used for diagnosing myocardial infarction. Bleeding will be assessed with the use of the GUSTO criteria.⁶⁷ Severe bleeding will be defined as fatal bleeding, intracranial hemorrhage, or bleeding causing hemodynamic compromise requiring blood or fluid replacement, inotropes, or surgery.⁶⁷ The frequencies of moderate bleeding, defined as bleeding requiring transfusion not characterized as severe, and moderate/severe and severe bleeding will also be analyzed. Information on (surgical or percutaneous) coronary revascularization will also be collected. Data will be entered on paper-based case report forms and will be double-entered into a secure, password protected database, accessible only by study personnel. Subjects will be identified by a unique study number in the database.

Additionally a Data Safety Monitoring Board will be appointed to review the study periodically (every 12 months, or sooner if required).

15. RISK/ BENEFIT ASSESSMENT:

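### The on-study anticoagulation stopping rule names only warfarin and dabigatran, leaving out the oral Xa inhibitors that exclusion criterion 3 treats as the same bleeding risk

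*Combined protocol and SAP*

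**What the plan says.** Section 14 (managing adverse reactions) contains the only on-study anticoagulation rule. Its trigger is "If a patient develops an indication for receiving oral anticoagulation therapy with warfarin or dabigatran during his or her participation in the study"; the action is to discontinue prasugrel, and the stated reason is bleeding risk. The two drugs are given as a closed list, with no wording to mark them as examples.

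Section 8, exclusion criterion 3, lists under increased bleeding risk "need for warfarin or oral Xa inhibitor or thrombin inhibitor administration". Section 12 (Randomization and Treatment) repeats the same three categories as an entry exclusion.

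Four other statements bear on the point:

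- Section 11: "All patients will be receiving aspirin, as per standard current practice".
- Section 14: a study role "will evaluate all adverse events and determine the appropriate course of action".
- Section 14, on severe bleeding: "prasugrel will be temporarily held and will be discontinued if the patient is considered to be at increased risk for recurrent bleeding".
- Section 12, on clinically indicated angiography before 10 months: "then prasugrel will be continued and the patient will be asked to return for the planned 12-month angiography".

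**The concern.** The protocol treats three kinds of anticoagulant as one bleeding hazard at entry, but its mandatory on-study stop names drugs from only two of them. The reason given for the stop applies equally to the third.

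Every patient takes aspirin. If someone starts an oral Xa inhibitor after randomization, and site staff follow the rule as written, a prasugrel-arm patient could continue on three antithrombotic drugs, a combination the protocol would have refused at entry. Severe bleeding is the primary safety endpoint, so the patients at risk are also those in whom that endpoint is most likely to occur.

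There is a lesser wording problem. The stopping rule, the severe-bleeding instruction and the early-angiography instruction all refer to prasugrel, although patients and coordinators are blinded. Taken literally they instruct one arm only. This is editorial, and the main point does not depend on it.

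**Working it through.** **Comparing the texts.** The plan states no figure on this point, so there is nothing to reproduce. The first check is a comparison of lists.

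| Category | Entry exclusion (section 8, criterion 3) | On-study stop (section 14) |
|---|---|---|
| Warfarin | named | named |
| Thrombin inhibitor | named | dabigatran named (an oral thrombin inhibitor) |
| Oral Xa inhibitor | named | not named |

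**Does anything else close the gap?**

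- Section 15 speaks of oral anticoagulants in general, but only in describing who is kept out of the study.
- In Table 2, the row "Inclusion/Exclusion criteria reviewed" is marked at time 0 only, so the entry criterion is not re-applied later.
- The adverse-event provision in section 14 allows a stop but does not require one, and starting an anticoagulant is not necessarily an adverse event.
- The Data Safety Monitoring Board (section 16) meets every 12 months and reviews aggregate adverse events. It does not direct individual treatment.

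**Size.** The only input from the documents is 60 patients per arm (section 13). The rest are assumptions, shown as ranges:

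- *p*, the share of patients who newly need an oral anticoagulant: 2–5%
- *s*, the share of those given an oral Xa inhibitor: 30–70%
- *f*, the share of those in whom the rule as worded does not fire: 0–100%. It is 0% if every such condition is also an indication for warfarin or dabigatran.
- *d*, the excess severe-bleed risk from continuing prasugrel on top of aspirin and an Xa inhibitor: 1–5 percentage points

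Prolonged-arm patients outside the rule = 60 × *p* × *s* × *f*, counted in the prasugrel arm:

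| *p* | *s* | *f* = 0 | *f* = 0.5 | *f* = 1 |
|---|---|---|---|---|
| 0.02 | 0.30 | 0 | 0.18 | 0.36 |
| 0.02 | 0.70 | 0 | 0.42 | 0.84 |
| 0.05 | 0.30 | 0 | 0.45 | 0.90 |
| 0.05 | 0.70 | 0 | 1.05 | 2.10 |

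- As a share of the arm, the maximum is 2.10 / 60 = 3.5%.
- Across both arms, the maximum is 2 × 2.10 = 4.2 patients.
- Excess severe bleeds at the maximum are 2.10 × 0.01 = 0.021 to 2.10 × 0.05 = 0.105.
- The chance of at least one excess bleed (Poisson) is at most 1 − exp(−0.105) ≈ 0.10.

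**The case against.** The strongest reply is that the rule already works in practice. Its trigger is an indication, not a prescription. If the condition that leads to an Xa inhibitor would also justify warfarin or dabigatran, the rule has fired whichever drug is chosen. The stated purpose points the same way, and reading the two names as letting Xa inhibitors through runs against it.

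Other provisions help. Section 12 allows unblinding when a complication occurs or clinical care requires it. Table 2 takes a medical history at every contact, so a new condition would probably be noticed, and it would often be an adverse event subject to the study's own review. Criteria 3 and 11 remove patients who already need anticoagulation and those with thromboembolism that prolongs the hospital stay, so only later onset counts. Finally, this is an abbreviated protocol that refers to an attached sponsor's protocol, which may have fuller wording.

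Most of this stands as an argument about size. It is why the lower end of the range is zero, and why the upper end, which needs every Xa-inhibitor patient to escape the rule, is unlikely. It does not close the gap: each provision permits a stop or makes one more likely, but none requires it. A mandatory safety stop should not depend on whether a clinician who chose an Xa inhibitor also judges that another drug was indicated. The sponsor's protocol was not supplied and cannot be checked.

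**Conclusion.** The concern holds for the wording of this document. Oral Xa inhibitors are the one anticoagulant category in criterion 3 with no counterpart in the on-study stopping rule, and no supplied text orders a stop for them. It is a drafting omission, neither a contradiction nor a sign that the combination was meant to be allowed.

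The effect is small and may be nil. The figures rest wholly on assumed rates, and unblinding or discretionary stops would lower them further. Confidence is high about the text but cannot extend to what sites would actually do. The change is worth making because it concerns patient safety and costs almost nothing. It has no bearing on power or on the choice of analysis.

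**What to change.** Replace the anticoagulation sentence in section 14 with wording such as:

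*If, while on study, a patient starts or develops an indication for any oral anticoagulant (warfarin, an oral Xa inhibitor or a thrombin inhibitor), study medication will be discontinued because of the bleeding risk.*

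Adding the start of treatment as a trigger removes the dependence on which drug was judged to be indicated. If the sponsor's protocol already has broader wording, align this text with it.

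As an optional consistency edit, change prasugrel to study medication, a term section 12 already uses, in the severe-bleeding instruction of section 14 and the early-angiography instruction of section 12. Blinded staff can then act in both arms.

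The cost is one reworded sentence and two word substitutions. On the assumptions above, it adds 0 to about 4 early discontinuations across both arms, a consequence the protocol already accepts for warfarin and dabigatran. Stopping the drug does not by itself remove a patient from the analysis, since section 13 states: "All endpoints (primary and secondary) will be analyzed with an intent-to-treat approach".

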22. DISSEMINATION OF RESEARCH RESULTS

The results from this research will be published in medical journals and presented at medical meetings.

23. MULTI-CENTER RESEARCH.

Not applicable.

REFERENCES, APPENDICES and TABLES:

Please see attached Sponsor's Protocol.
